### Attachment 7: Snaith-Hamilton Pleasure Scale (SHAPS)

	This questionnaire is designed to measure your ability to experience pleasure in the last few days . It is important to read each statement very carefully . Tick one of the boxes  to indicate how much you agree or disagree with each statement.
1.	I would enjoy my favourite television or radio programme
	Strongly disagree
	Disagree
	Agree
	Strongly agree
2.	I would enjoy being with my family or close friends
	Definitely agree
	Agree
	Disagree
	Strongly disagree
3.	I would find pleasure in my hobbies and pastimes
	Strongly disagree
	Disagree
	Agree
	Strongly agree
4.	I would be able to enjoy my favourite meal
	Definitely agree
	Agree
	Disagree
	Strongly disagree
5.	I would enjoy a warm bath or refreshing shower
	Definitely agree
	Agree
	Disagree
	Strongly disagree
6.	I would find pleasure in the scent of flowers or the smell of a fresh sea breeze or freshly baked bread
	Strongly disagree
	Disagree
	Agree
	Strongly agree
7.	I would enjoy seeing other people's smiling faces
	Definitely agree
	Agree
	Disagree
	Strongly disagree

8.	I would enjoy looking smart when I have made an effort with my appearance
	Strongly disagree
	Disagree
	Agree
	Strongly agree
9.	I would enjoy reading a book, magazine or newspaper
	Definitely agree
	Agree
	Disagree
	Strongly disagree
10.	I would enjoy a cup of tea or coffee or my favourite drink
	Strongly disagree
	Disagree
	Agree
	Strongly agree
11.	I would find pleasure in small things e.g. a bright sunny day, a telephone call from a friend
	Strongly disagree
	Disagree
	Agree
	Strongly agree
12.	I would be able to enjoy a beautiful landscape or view
	Definitely agree
	Agree
	Disagree
	Strongly disagree
13.	I would get pleasure from helping others
	Strongly disagree
	Disagree
	Agree
	Strongly agree
14.	I would feel pleasure when I receive praise from other people
	Definitely agree
	Agree
	Disagree
	Strongly disagree

Reproduced from: Snaith et al. (1995) A scale for the assessment of hedonic tone. The Snaith-Hamilton Pleasure Scale. *British Journal of Psychiatry*, **167**, 99-103.

 $\odot$  1995 The Royal College of Psychiatrists. Written permission must be obtained from the Royal College of Psychiatrists for copying and distribution to others or for republication (in print, online or by any other medium).

#### Attachment 8: Quality of Life Enjoyment and Satisfaction Questionnaire (Q-LES-Q)

Name:

Date:

#### Quality of Life Enjoyment and Satisfaction Questionnaire – Short Form (Q-LES-Q-SF)

Taking everything into consideration, during the past week how satisfied have you been with your.....

	Very Poor	Poor	Fair	Good	Very Good
physical health?	1	2	3	4	5
mood?	1	2	3	4	5
work?	1	2	3	4	5
household activities?	1	2	3	4	5
social relationships?	1	2	3	4	5
family relationships?	1	2	3	4	5
leisure time activities?	1	2	3	4	5
ability to function in daily life?	1	2	3	4	5
sexual drive, interest and/or performance?*	1	2	3	4	5
economic status?	1	2	3	4	5
living/housing situation?*	1	2	3	4	5
ability to get around physically without feeling dizzy or unsteady or falling?*	1	2	3	4	5
your vision in terms of ability to do work or hobbies?*	1	2	3	4	5
overall sense of well being?	1	2	3	4	5
medication? (If not taking any, check here and leave item blank.)	1	2	3	4	5
How would you rate your overall life satisfaction and contentment during the past week?	1	2	3	4	5

\*If satisfaction is very poor, poor or fair on these items, please UNDERLINE the factor(s) associated with a lack of satisfaction.

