5.1.2. Imputation Methods for Missing Items

Imputation of missing individual items will apply only to the LSAS, as described in Section 5.2.1. For all other scales where multiple items are summed to create a total score, if any item of the scale is missing on a visit, the total score for that scale at that visit will be left blank.

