5.4.1.5. Q-LES-Q

The Quality of Life, Enjoyment, and Satisfaction Questionnaire (Q-LES-Q) is a 16-item self-administered questionnaire designed to measure degree of enjoyment and satisfaction in general activities. The Q-LES-Q measures each of the items using a 5-point Likert-type scale as: 1=very poor; 2=poor; 3=fair; 4=good; 5=very good. The scoring of the Q-LES-Q involves summing only the first 14 items to yield a raw total score. The last 2 items are not included in the total score but are stand-alone items. The raw total score ranges from 14 to 70. The raw total score is transformed into a percentage maximum possible score using the following formula:

$$100 * \frac{(\text{raw total score} - \text{minimum possible raw score})}{(\text{maximum possible raw score} - \text{minimum possible raw score})}$$

The minimum possible raw score on the Q-LES-Q is 14, and the maximum possible raw score is 70. Higher Q-LES-Q scores reflect greater enjoyment and satisfaction with general activities.

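### Read literally, the SAP's missing-item rule blanks a complete 14-item Q-LES-Q total when the unscored medication item is left blank as the form instructs

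*Protocol*

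**What the plan says.** Three places bear on this.

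- **The form (Protocol Attachment 8).** The short-form Q-LES-Q has 16 rows. Row 15 asks about satisfaction with "medication? (If not taking any, check here and leave item blank".
- **The missing-item rule (SAP 5.1.2).** "Imputation of missing individual items will apply only to the LSAS". Then: "For all other scales where multiple items are summed to create a total score", the instruction is that "if any item of the scale is missing on a visit, the total score for that scale at that visit will be left blank".
- **The scoring rule (SAP 5.4.1.5).** The Q-LES-Q "is a 16-item self-administered questionnaire". "The scoring of the Q-LES-Q involves summing only the first 14 items to yield a raw total score", and "The last 2 items are not included in the total score but are stand-alone items".

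SAP 5.4.2 then summarises actual values and changes from baseline of the percentage maximum score. It tabulates the last two items separately as frequencies.

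**The concern.** SAP 5.1.2 ties the blank total to items of the scale, not to items in the sum. For most scales in the SAP the two coincide. For the Q-LES-Q they do not: the SAP counts 16 items in the questionnaire and sums 14.

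One of the two unsummed items is blank by design for anyone taking no medicine. That blank is a correct response to the form, not a skipped rating, and it says nothing about whether the 14 scored items are usable. Neither SAP 5.1.2 nor SAP 5.4.1.5 exempts items 15 and 16 or says how a ticked box is to be treated. Two careful programmers could therefore produce different Q-LES-Q tables from the same data.

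What is at stake is the Q-LES-Q change from baseline, which Protocol 9.3.2 lists as an exploratory endpoint and which serves the quality-of-life objective.

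**Working it through.** **1. Reproduce the SAP's own range.** Fourteen items scored 1 to 5 give 14 × 1 = 14 to 14 × 5 = 70, which is the range in SAP 5.4.1.5. Sixteen items would give 16 to 80. So the total excludes items 15 and 16, and the medication item is the fifteenth row of the form.

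**2. Score one record under both readings.** Take items 1 to 14 each answered 3, item 15 blank with the box ticked, and item 16 answered 3.

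| Reading of SAP 5.1.2 | Items checked | Result |
|---|---|---|
| Literal: any of the 16 items | 1–16 | item 15 is blank, so no total |
| Restricted: items that are summed | 1–14 | raw total 14 × 3 = 42; 100 × (42 − 14)/(70 − 14) = 50.0 |

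The data are identical, and the only difference is an item that neither calculation adds up.

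**3. When the blank can occur.** Protocol 9.1.3 places the Q-LES-Q among the Day 1 assessments done before dosing. Protocol 4.2 and Section 8 bar or wash out psychotropic drugs, so some subjects may be taking nothing that day. After the first dose, subjects are on study medication and can answer item 15. A possible exception is someone who has stopped treatment and returns for the final assessments that Protocol 10.2 requests.

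**4. Whether the baseline can be recovered.** SAP 2.3.3 takes the last non-missing value before first dose. The Time and Events Schedule has no Q-LES-Q at screening, and the Q-LES-Q windows in SAP Table 2 start at the baseline visit. There is nothing to fall back on, so a blank Day 1 total means no change score at Weeks 4, 8 or 12.

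**5. How many subjects.** The documents do not give the share taking no medicine on Day 1. To show only how the count scales, take 122 subjects: the 137 planned in Protocol 11.2 less the 15 (7 + 8) that SAP 2.5.3 leaves out of the ITT set. For an assumed share f, the number losing change scores is 122 × f.

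| Assumed share f | Lose change scores | Keep them |
|---|---|---|
| 20% | 24 | 98 |
| 40% | 49 | 73 |
| 60% | 73 | 49 |
| 80% | 98 | 24 |

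No row of this table is better supported by the documents than another.

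**The case against.** The best defence is that the SAP should be read as a whole. SAP 5.1.2 is a general rule about totals made by summing items. SAP 5.4.1.5 is the specific rule, and it sets items 15 and 16 apart as stand-alone, with their own frequency table in SAP 5.4.2. On that reading a total is blank only if one of its own items is missing. Moreover, a subject who ticks the box has given an answer, and the SAP does not say that a documented not-applicable response counts as missing. The loss therefore needs two unfavourable readings together. This stands as a reason not to say that totals will be voided. It does not remove the point, because the text of SAP 5.1.2 says otherwise and no sentence settles it.

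A reader might also infer that much of the Q-LES-Q data would go. The documents do not support that. Item 15 asks about medication in general, and the protocol admits subjects on treatment for stable conditions, on treated thyroid disease, on hormonal contraception and on as-needed non-benzodiazepine sleep aids. Barring psychotropic drugs does not make a subject unmedicated.

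Nor is there support for a loss of power or a bias between arms. SAP 5.4.2 plans no model or test for this endpoint. Taking some other medicine on Day 1 is settled before the first dose, so the selection is not caused by treatment. What remains is that the change scores could describe a smaller subset, made up of subjects who were taking some medicine at entry.

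**Conclusion.** The point holds as a defect of wording with a small, avoidable consequence. If SAP 5.1.2 is followed literally and a ticked box is treated as missing, subjects on no medicine at Day 1 lose a complete 14-item baseline total and, with it, every Q-LES-Q change score. Both conditions are assumptions about how the rule would be programmed, and the number of subjects is unknown.

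The reach is limited. Actual values at Weeks 4, 8 and 12 would largely remain. The summaries affected are descriptive and concern one exploratory scale. The primary LSAS analysis and the secondary endpoints are untouched. Severity: minor.

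**What to change.** In SAP 5.1.2, make the trigger for a blank total a missing item that enters that total, and state that for the Q-LES-Q these are items 1 to 14. Nothing changes for a scale whose total sums all its items, and no total that is valid under the current wording is altered.

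In the SAP 5.4.2 frequency table for the last two Q-LES-Q items, report a ticked box on item 15 as not applicable, where the box is captured. The documents do not say whether it is. If it is not, the blank can be shown as such in that table, and the correction to the total still works.

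The cost is one amended sentence and, at most, one extra category in a table. No new data are needed.

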#### Attachment 9: Self-Assessment of Treatment Experience

These questions are about your overall experience while on the study medication. Please answer each question by selecting the response that best describes you.

1. Considering all aspects of your depression, since starting this study medication, overall would you say your depression is:

### (Select one response)

- □ Very much improved
- □ Much improved
- □ Improved (just enough to make a difference)
- $\Box$  No change
- □ Worse (just enough to make a difference)
- □ Much worse
- □ Very much worse

#### 2. Please select your response to the following statements.

	Yes	No
While taking the study medication:		
I felt more relaxed		
My mood improved		
I was better able to perform my daily activities		
I felt more interested in social activities		
My sleep improved		
I felt less distracted		

3. During the past week (7 days), how would you rate your appetite (your overall desire to eat)?

### (Select one response)

- □ Very good
- Good
- **Fair**
- Poor
- □ Very poor

### 4. How interested would you be in continuing to take the study medication if needed?

### (Select one response)

- Not at all interested
- A little interested
- □ Moderately interested
- □ Very interested
- Extremely interested

### Attachment 10: Columbia Suicide Severity Rating Scale – BASELINE

SUICIDAL IDEATION					
Ask questions 1 and 2. If both are negative, proceed to "Suicidal Behavior" section. If the answer to question 2 is "yes," ask questions 3, 4 and 5. If the answer to question 1 and/or 2 is "yes", complete "Intensity of Ideation" section below.	Time I Felt	ime: He/She Most iidal			

 
Wish to be Dead Subject endorses thoughts about a wish to be dead or not alive anymore, or wish to fall askeep and not wake up. Have you wished you were dead or wished you could go to sleep and not wake up?
 
	Yes	No □			
If yes, describe:					
2. Non-Specific Active Suicidal Thoughts General, non-specific thoughts of wanting to end one's life/commit suicide (e.g. 'I've thought about killing myself'') without thoughts of ways to kill oneself/associated methods, intent, or plan. Have you actually had any thoughts of killing yourself?	Yes	No □			
If yes, describe:					
3. Active Suicidal Ideation with A ny Methods (Not Plan) without Intent to Act Subject endorses thoughts of suicide and has thought of at least one method during the assessment period. This is different than a specific plan with time, place or method details worked out (e.g. thought of method to kill self but not a specific plan). Includes person who would say, "I shought about taking an overdose but never made a percific plane at to when, where or how I would actually do it, and I would never go through which it". Have you been thinking about how you might do this?					
If yes, describe:					
4. Active Suicidal Ideation with Some Intent to Act, without Specific Plan Active suicidal thoughts of killing oneself and subject reports having some intent to act on such thoughts , as opposed to "I have the thoughts but I definitely will not do anything about them". Have you had these thoughts and had some intention of acting on them?	Yes	No □			
If yes, describe:					
5. Active Suicidal Ideation with Specific Plan and Intent Thoughts of killing oneself with details of plan fully or partially worked out and subject has some intent to carry it out. Have you started to work out or worked out the details of how to kill yourself? Do you intend to carry out this plan?	Yes	No □			
If yes, describe:		_			
INTENSITY OF IDEATION	I				
The following features should be rated with respect to the most severe type of ideation (i.e., $1-5$ from above, with $1$ being the least severe					

A ctual Attempt: A potentially self-injurious act committed with at least some wish to die, an a result of act . Behavior was in part thought of as method to kill oneself. Intent does not have to be 100%. If there is any intent/desire to die associated with the act, then it can be considered an actual suicide attempt. There does not				No □
have to be any injury or harm, just the potential for injury or harm. If person pulls trigger while gun is in mouth but g this is considered an attempt.	-			
Inferring Intent: Even if an individual deries intent/wish to die, it may be inferred clinically from the behavior or circumsta act that is clearly not an accident so no other intent but suicide can be inferred (e.g. gunshot to head, jumping from window someone denies intent to die, but they thought that what they did could be lettal, intert may be inferred.				
Have you made a suicide attempt?				
Have you done anything to harm yourself? Have you done anything dangerous where you could have died?			Total	# of
What did you do?			Atter	npts
Did youas a way to end your life? Did you want to did (any a little) when you			_	_
Did you want to die (even a lätle) when you? Were you trying to end your life when you?				
Or did you think it was possible you could have died from?				
Or did you do it purely for other reasons / without ANY intention of killing yourself (like to relieve str	ess, feel be#ei	r, get sympathy	,	
or get something else to happen)? (Self-Injurious Behavior without suicidal intent) If yes, describe:				
- /,			Yes	No
Has subject encoded in Non-Suisidel Self Injurious Behavior?				
Has subject engaged in Non-Suicidal Self-Injurious Behavior? Interrupted Attempt:			 	_
When the person is interrupted (by an outside circumstance) from starting the potentially self-injurious act (if not for that, a	cual avempt wo	uld have	Yes	No
occurred). Overdose: Person has pills in hand but is stopped from ingesting. Once they ingest any pills, this becomes an attempt rathe	r than an interrup	ied attempt.		
Shooting: Person has gun pointed toward self, gun is taken away by someone else, or is somehow prevented from pulling tr	igger, Once they	pull the trigger,		
even if the gun fails to fire, it is an attempt. Jumping: Person is poised to jump, is grabbed and taken down from ledge. Han but has not yet started to hang - is stopped from doing so.	ging: Person has	noose around neck	Total	# of
Has there been a time when you started to do something to end your life but someone or something st	opped you bej	ore you	intern	
actually did anything? If yes, describe:				_
a yes, describe.			-	_
A borted Attempt:			Yes	No
When person begins to take steps toward making a suicide attempt, but stops themselves before they actually have engaged Examples are similar to interrupted attempts, except that the individual stops him/herself, instead of being stopped by some		uctive behavior.		
Has there been a time when you started to do something to try to end your life but you stopped yourse		actually did		
anything? If yes, describe:			Total abor	
a yes, associate.				
Preparatory Acts or Behavior:			+-	
A cts or preparation towards imminently making a suicide attempt. This can include anything beyond a verbalization or thou		mbling a specific	Yes	No
method (e.g. buying pills, purchasing a gun) or preparing for one's death by suicide (e.g. giving things away, writing a suic Have you taken any steps towards making a suicide attempt or preparing to kill yourself (such as coll		tting a otta		
giving valuables away or writing a suicide note)?	eening pias, ge	tong a gon,		
If yes, describe:				
Suicidal Behavior:			Yes	No
Suicidal behavior was present during the assessment period?				
A menung for A stud Attempts Only	Most Recent	Most Lethal	Initial/Fig	
Answer for Actual Attempts Only	Attempt	Attempt	Attempt	
A ctual Lethality/Medical Damage:	Date: Enter Code	Date: Enter Code	Date: Enter	Cade

No physical damage or very minor physical damage (e.g. surface scratches).

	Enter Coure	EnterCode	EALO	Loue

 
Minor physical damage (e.g. lethargic speech; first-degree burns; mild bleeding; sprains).
 
Moderate physical damage; medical attention needed (e.g. conscious but sleepy, somewhat responsive; second-degree
 
				
burns; bleeding of major vessel).				

 
Moderately severe physical damage; medical hospitalization and likely intensive care required (e.g. comatose with reflexes intact; third-degree burns less than 20% of body; extensive blood loss but can recover; major fractures).
 
		—	-	_
4. Severe physical damage; medical hospitalization with intensive care required (e.g. comatose without reflexes; third-				
degree burns over 20% of body; extensive blood loss with unstable vital signs; major damage to a vital area). 5. Death				
Potential Lethality: Only Answer if Actual Lethality=0	Enter Code	Enter Code	Enter	Code
Likely lethality of actual attempt if no medical damage (the following examples, while having no actual medical damage, had potential for very serious lethality, put gun in mouth and pulled the trigger but gun fails to fire so no medical damage;				
laying on train tracks with oncoming train but pulled away before run over).				
0 - Behavior not likely to result in injury			_	

 
Behavior likely to result in injury but not likely to cause death
 
				_
2 - Behavior likely to result in death despite available medical care				

### Attachment 11: Columbia Suicide Severity Rating Scale – Since Last Visit

SUICIDAL IDEATION			
isk questions 1 and 2. If both are negative, proceed to "Suicidal Behavior" section. If the answer to question 2 is "yes," sk questions 3, 4 and 5. If the answer to question 1 and/or 2 is "yes", complete "Intensity of Ideation" section below.		Since Last Visit	

 
Wish to be Dead Subject endones thoughts about a wish to be dead or not alive anymore, or wish to fall asleep and not wake up. Hare you wished you were dead or wished you could go to sleep and not wake up?
 
		Yes	No □
If yes, describe:			

 
Non-Specific Active Suicidal Thoughts General non-specific thoughts of wanting to end one's life/commit suic
 
	tide (e.g. "I've though about killing myself") without thoughts of ways to kill	Yes	No
oneself/associated methods, intent, or plan during the assessment period Hare you actually had any thoughts of killing yourself?			
If yes, describe:			

 
Active Suicidal Ideation with Any Methods (Not Plan) Subject endorses thoughts of suicide and has thought of at least one me place or method details worked out (e.g. thought of method to kill self overdose but I never made a specific plan as to when, where or how I w Hare you been thinking about how you might do this?
 
	thod during the assessment period. This is different than a specific plan with time, but not a specific plan). Includes person who would say, "I thought about taking an	Yes	No □
If yes, describe:			
4. Active Suicidal Ideation with Some Intent to Act, with Active suicidal thoughts of killing oneself and subject reports having so definitely will not do anything about them". Hare you had these thoughts and had some intention of acting on the	ane intent to act on such thoughts, as opposed to "I have the thoughts but I	Yes	No □
If yes, describe:			

 
Active Suicidal Ideation with Specific Plan and Intent Thoughts of killing oneself with details of plan fully or partially worker Hare you started to work out or worked out the details of how to kill y
 
	d out and subject has some intent to carry it out,	Yes	No □
If yes, describe:			
INTENSITY OF IDEATION			
The following features should be rated with respect to the most and 5 being the most severe ).	severe type of ideation (i.e., $l$ -5 from above, with $l$ being the least severe	м	ost
Most Severe Ideation:		Ser	vere
Type#(1-5)	Description of Ideation		

neck but has not yet started to hang - is stopped from doing so.	Total# of
Has there been a time when you started to do something to end your life but som eone or something stopped you before you	interrupted
actually did anything? If yes, describe:	
n pay a second	—
Aborted Attempt:	Yes No
When person begins to take steps toward making a suicide attempt, but stops themselves before they actually have engaged in any self-destructive behavior.	
Examples are similar to interrupted attempts, except that the individual stops him/herself, instead of being stopped by something else.	
Has there been a time when you started to do something to try to end your life but you stopped yourself before you	Total # of
actually did anything? If yes, describe:	aborted
n jes, waine	
Preparatory Acts or Behavior:	
Acts or preparation towards imminently making a suicide attempt. This can include anything beyond a verbalization or thought, such as assembling a	Yes No
specific method (e.g. buying pills, purchasing a gun) or preparing for one's death by suicide (e.g. giving things away, writing a suicide note).	
Have you taken any steps towards making a suicide attempt or preparing to kill yourself (such as collecting pills, ge#ing a gun,	
giving valuables away or writing a suicide note)? If yes, describe:	
n yex, describe.	
Suicidal Behavior:	Yes No
Suicidal behavior was present during the assessment period?	
Consisted Society	Yes No
Completed Suicide:	
Answer for Actual Attempts Only	Most Lethal Attempt
	Date:
Actual Lethality/Medical Damage:	Enter Code

 
No physical damage or very minor physical damage (e.g. surface scratches).
 
Minor damage of a biblioging damage (e.g. surface scratches).
 
	

 
Minor physical damage (e.g. lethargic speech; first-degree burns; mild bleeding; sprains).
 
Moderate physical damage; medical attention needed (e.g. conscious but skeeps, somewhat responsive; second-degree burns; bleeding of major vessel).
 
	
3. Moderately severe physical damage; msdical hospitalization and likely intensive care required (e.g. comatose with reflexes intact; third-degree burns less	
than 20% of body; extensive blood loss but can recover; major fractures).	

 
Severe physical damage; medical hospitalization with intensive care required (e.g. comatose without reflexes; third-degree burns over 20% of body; extensive blood loss with unstable vital signs; major damage to a vital area).
 
	
5. Death	
	Enter Code
Potential Lethality: Only Answer if Actual Lethality=0	and a second
Likely lethality of actual attempt if no medical damage (the following examples, while having no actual medical damage, had potential for very serious	1
Likely lethality of actual attempt if no medical damage (the following examples, while having no actual medical damage, had potential for very serious lethality: put gun in mouth and pulled the trigger but gun fails to fire so no medical damage; laying on train tracks with oncoming train but pulled away	
Likely lethality of actual attempt if no medical damage (the following examples, while having no actual medical damage, had polential for very serious lethality: put gun in mouth and pulled the trigger but gun fails to fire so no medical damage; laying on train tracks with oncoming train but pulled away before run over).	
Likely lethality of actual attempt if no medical damage (the following examples, while having no actual medical damage, had potential for very serious lethality: put gun in mouth and pulled the trigger but gun fails to fire so no medical damage; laying on train tracks with oncoming train but pulled away	

